6.2 Subject Exclusion Criteria

1. Patients who have had prior abdominal radiotherapy.
2. Patients receiving any investigational agents.
3. Uncontrolled intercurrent illness including, but not limited to, ongoing or active infection, symptomatic congestive heart failure, unstable angina pectoris, cardiac arrhythmia, or psychiatric illness/social situations that would limit compliance with study requirements.
4. Contraindication to IV contrast
5. Patients in which iodine contrast is contraindicated.
6. Pregnant and breastfeeding women are excluded. Women of childbearing potential who are unwilling or unable to use an acceptable method of birth

control to avoid pregnancy for the entire study period and for up to 4 weeks after the study are excluded. This applies to any woman who has experienced menarche and who has not undergone successful surgical sterilization or is not postmenopausal (defined as amenorrhea for at least 12 consecutive months, or women on hormone replacement therapy with serum FSH levels greater than 35 mIU/mL. A negative urine or serum pregnancy test must be obtained within 14 days prior to the start of study therapy in all women of childbearing potential. Male subjects must also agree to use effective contraception for the same period as above.

7.0 RECRUITMENT PLAN

This study will be available to all patients seen at University of Colorado who meet the eligibility criteria. University of Colorado is a referral center for pancreatic cancer and all patients considered for this study will be presented at a weekly multidisciplinary Pancreatic Multidisciplinary Conference. In addition, the study will be placed on the University of Colorado Website to maximize patient recruitment. Patients will be identified from surgical, gastroenterology and medical oncology clinics for treatment of their disease. The investigators take due notice of the NIH policy concerning inclusion of women and minorities in clinical research populations.

Patient recruitment will continue for a period of 3 years. Based on past census values at University of Colorado, we expect 10-15 local pancreatic cancer patients will be eligible for this study per year. The target accrual is 18 patients over 3 years.

8.0 PRETREATMENT EVALUATIONS (PRE-SCREENING)

To be completed:

- Histologic or cytologic confirmation of malignancy.
- Endoscopic retrograde cholangiopancreatography (ERCP) as clinically indicated for placement of a biliary stent for obstructive jaundice and/or for brushings/washings to confirm malignancy.
- Endoscopic ultrasonography (EUS) will be performed. Cytologic confirmation of malignancy will be obtained during EUS by core biopsy or Fine Needle Aspiration (FNA), if possible.
- A 12-lead Electrocardiogram (EKG).
- Within 2-4 weeks of completion of induction chemotherapy (at least 3 months but no more than 12 months of standard of care chemotherapy for LAPC, either FOLFIRINOX or gemcitabine and nab-paclitaxel), patients will be evaluated with a repeat CT of the chest, abdomen and pelvis with a dedicated pancreatic protocol/angiogram series. If there is no evidence of distant disease and the pancreatic

tumor is still deemed to be unresectable by a hepatobiliary surgeon, the patient may be eligible for the protocol. If the patient is eligible and enrolled on the study, treatment should be initiated within 30 days of the CT scan or it must be repeated.

- Patients will be seen by a radiation oncologist to discuss the radiotherapy options and if the tumor is felt to be amenable to SBRT, the patient can be enrolled on the dose escalation protocol.

9.0 STUDY PROCEDURES - SCREENING

9.1 To be completed within 30 days prior to SBRT:

- History and physical examination and performance status.
- CT chest, abdomen, pelvis with a dedicated pancreatic protocol.
- Review of CT or MRI scans at Multidisciplinary Conference to determine if tumor is locally advanced.
- Documentation of all measurable or non-measurable disease parameters including radiographic imaging procedures within four weeks of study entry. The definitions of measurable and non-measurable disease will be those definitions used in the RECIST criteria as defined by CTEP (<http://ctep.info.nih.gov/Policies>).
- Placement of gold fiducial markers (via EUS or, if not feasible by EUS, by direct visualization under laparoscopy). No specific location within the tumor is required. In conjunction with the imaging system, fiducials will serve to identify the precise location of the pancreas tumor relative to these markers during SBRT and confirm that the tumor does not move significantly with respect to the bony skeleton over the course of treatment. It is expected that such fiducial placement will be done on an outpatient basis. If the patient has a plastic stent, this can be exchanged for a metal wall stent.
- Core biopsy or Fine Needle Aspiration (FNA) will be obtained during EUS if possible -The sample will be sent for immunomonitoring assays.
- Complete blood count (CBC) with differential and platelet count, serum chemistries (Na, Cl, BUN, Creatinine, K, Bicarb, and glucose), LFTs (AST, ALT, alkaline phosphatase, total bilirubin), calcium, albumin, total protein, LDH, INR and CEA, CA19-9.

9.2 To be completed within 14 days prior to SBRT:

- Serum pregnancy test for all women of childbearing potential. If the test result is positive, the patient will not be allowed to participate in this study.
- Research blood draw for immune monitoring analysis
- Completion of quality of life (QOL) assessment

- Simulation for radiotherapy planning: At least 4 days after the fiducial placement, patients will undergo a simulation for RT treatment planning at which time the patient is immobilized in a cradle. While immobilized, a thin-sliced CT with IV and PO contrast is performed. A 4DCT scan is obtained for patients treated with respiratory gating (see section 4.2). A pCT will also be performed in the treatment position.

10.0 STUDY PROCEDURES - TREATMENT/INTERVENTION PLAN

- The interval between completion of induction chemotherapy and initiation of SBRT should be preferably within 2-4 weeks but no longer than 8 weeks.
- Based on the planning CT scan performed at the simulation, an SBRT treatment plan is developed using inverse planning methods. A dose distribution in which the target receives the prescription dose, and the relevant normal tissues are exposed to less than the tolerance dose levels is evaluated. VMAT arc therapy or multi-field IMRT plans will be acceptable.
- A total dose of 900cGy will be delivered to the tumor with each fraction for the first 3-patient cohort. Dose escalation will start with dose level 1 (9 Gy x 3 fractions) and increase by 1 Gy per fraction at each dose level, dose level 2 will be 10 Gy x 3 fractions and dose level 3 will be 11 Gy x 3 fractions.
- Motion management will be achieved by either placement of an abdominal compression belt or using respiratory gating per standard of care.
- At the time of treatment, kilo voltage images are taken to evaluate positioning based on the fiducial markers.
- Initial shifts are made to bring the patient into the correct position.
- A cone beam CT (CBCT) scan is performed.
- The CBCT scan is registered with the planning CT scan in 3D by aligning the fiducial markers from the two scans.
- The position of the fiducial markers or stent on the simulation CT is then compared with the position of the fiducial markers or stent seen in the CBCT scan. Any adjustment to the position of the volume to be treated is made by the physician using software developed for this purpose.
- If an adjustment is to be made, it is implemented by correcting the position of the treatment couch.
- A second CBCT scan is taken to confirm patient is in the correct treatment position. Any additional shifts can be made as needed.
- A 2D-KV orthogonal pair is obtained for confirmation of treatment position
- The first fraction of SBRT is then delivered.

- A pCT is performed within 90 minutes of SBRT.
- 2 more fractions of SBRT are delivered.
- A pCT is performed at 6 weeks post SBRT.
- Research blood draw during SBRT and at 6 weeks follow-up.

10.1 Research Samples

A research biopsy will be performed prior to treatment to analyze tumor and stromal expression of biomarkers and correlate these with clinical outcomes. The biopsy will be performed, if possible, at the time of the EUS-guided fiducial placement. The research coordinator will bring the tissue in formalin directly to research histology. Research histology will embed the biopsy to deliver the de-identified sample to the Human Immune Monitoring Shared Resource for further analyses. Peripheral blood will be prior to SBRT treatment, during SBRT treatment, and 6 weeks following treatment according to the schedule outlined in section 11. Two 8 ml EDTA blood tubes will be collected at each time point for experimental research that will be performed in the University of Colorado Denver School of Medicine Human Immune Monitoring Shared Resource. Blood samples will be de-identified prior to transfer to the Human Immune Monitoring Shared Resource using study numbers that will be assigned to each blood sample in the order they are drawn. A sample information form will be included with each sample describing the de-identified study number, the time the blood was drawn, and the time the blood was submitted. All research samples will be labeled with de-identified study numbers. The PI will maintain a secure record of patient and study ID's.

10.2 Specimen Analysis

Peripheral blood mononuclear cells (PBMCs) will be isolated and flow cytometry will be used to quantify immune cell phenotypes, to measure tumor-specific T cell responses, and to measure cytokines present in plasma. Biopsy samples from the primary pancreas tumor will be obtained by fine needle aspiration and if feasible, core needle biopsy by the gastroenterologists at the time of fiducial placement. Specimen processing will be performed by the Tissue Banking Shared Resource and submitted for further analyses as described below by the Human Immune Monitoring Shared Resource.

- **Baseline and post-treatment immune monitoring.** Participants will be asked to provide 16 mls of blood prior to initiating treatment, during treatment, and after completion of treatment to evaluate changes in immune cell frequency and activation status by flow cytometry. Approximately five million PBMCs will be used to determine the frequency of tumor-specific T cell responses by stimulating the cells with a mixture of peptides derived from known tumor antigens and measuring IFN-gamma production by ELISPOT.

Approximately five million PBMCs will be used to analyze the frequency of T cell populations and their activation status by flow cytometry. Any remaining cells will be securely stored for up to five years.

- **Cytokine analysis.** Up to 10 ml of plasma will be securely stored for five years following study completion for subsequent cytokine analysis. Multiplex cytokine array will be used for subsequent cytokine analysis. Concentration of cytokines related to the function of MDSCs (GM-CSF, VEGF, MIP-1 alpha, MIP-1 beta, IL-10, IL-6, and IL-8) and T cells (IFN-gamma, TNF-alpha, IL-1-beta, IL-2, IL-4, IL-5, IL-12p70, IL-17) will be analyzed.
- **Tissue analysis:** Immune cells will also be quantified and characterized in tumor biopsies using the Vectra 3 imaging system that enables immunohistochemical analysis of up to six immune markers (plus DAPI) in formalin-fixed paraffin-imbedded tissue samples on a single slide. The powerful accompanying inForm software uses trainable algorithm-based tools to recognize and segment tissue morphology, phenotype and quantify infiltrating immune cells, score positive regions in the tissue, and provide mean fluorescence intensities and two-dimensional geometric locations for each cell in the tissue.

11.0 EVALUATION DURING TREATMENT/INTERVENTION

Tests/Procedures	Before SBRT		During SBRT ⁵	Follow-up					
	Within 30 days	Within 14 days		6 wks ± 1 wk	10-12 wks	6 mos±2 wks	9 mos±2 wks	12 mos±2 wks	18 and 24 months ± 4 wks
Placement of gold fiducial markers + EUS-guided FNA or core biopsy	X								
Review at Multidisciplinary Conference	X								
Medical History	X ⁷				X	X	X	X	X
Physical Exam and ECOG⁶	X				X	X	X	X	X
CBC, Metabolic panel, LFTs, Ca-19-9, CEA	X			X	X	X	X	X	X
Pregnancy test¹		X ¹							
Research Blood		X	X	X					
CT (chest, abd & pelvis)	X ³				X	X	X	X	X
Simulation CT, 4DCT⁴		X							
Cone beam scan			X						
Abdominal pCT		X	X ²	X					
3 fractions of SBRT delivered			X						
Toxicity Assessments		X	X	X	X	X	X	X	X
EORTC QLQ-C30, EORTC QLQ-PAN26		X			X	X			
Survival Status									

¹ For women of child bearing potential

² To be performed within 30-120 minutes following the first fraction of SBRT

³ CT scans of the chest/abdomen/pelvis can be done prior to enrollment but must be within 30 days of initiating SBRT.

⁴ For respiratory gating patients only

⁵ Set-up and treatment procedure repeated for each of 3 fractions

⁶ Physical exam includes HEENT, Pulmonary, Cardiovascular, GI/Abdomen, Extremities, Neurological, Skin and hair

⁷ Including smoking history

12.0 TOXICITIES/SIDE EFFECTS

12.1 Preparation for SBRT

Toxicities may occur from the pancreas core biopsies and placement of the fiducial markers. Potential adverse effects include cholangitis, pancreatitis, bleeding, and infection.

All patients will get standard antibiotic prophylaxis at the time of biopsy.

12.2 SBRT planning and treatment

No side effects are expected to result from the CB imaging used for on-line target localization. The additional patient dose from the two cone beam scans is approximately 10 cGy, which represent less than 1% of the prescription dose.

Toxicities will be assessed using the NCI Common Terminology Criteria for Adverse Events version 4.0 (CTCAE v 4.0). Possible toxicities may occur from the single fraction high dose treatment include:

12.2.1 Anticipated Toxicities of SBRT

Likely:

- stomach pain and intestinal discomfort
- abdominal bloating and gas
- nausea
- diarrhea
- fatigue
- tanning
- skin redness
- hair loss within the radiation area - which is temporary
- permanently dry skin in the radiation treatment area
- loss of appetite and weight loss
- mild muscle aches in the area treated

Less Likely:

- vomiting
- low blood counts, which could lead to an increased risk of infection
- weakness and/or bleeding and bruising easily

Rare, but serious:

- change in liver or kidney function, which is unlikely to cause symptoms

- bowel obstruction, which could result in abdominal pain, nausea and vomiting and may require surgery
- gastric, duodenal or small-bowel ulcer formation that can result in abdominal pain, nausea and vomiting, and bleeding, and may require surgery

The risk of significant toxicity would depend on the presence of normal tissue structures in close proximity to the target. These normal tissue doses will be constrained by the treatment plan to deliver doses no more than those listed in section 4.2 (Intervention: Radiation Treatment Planning).

Patients will be assessed for late toxicities (>3 months post radiation) every 3 months for the first year.

13.0 CRITERIA FOR THERAPEUTIC RESPONSE/OUTCOME ASSESSMENT

13.1 Primary objective:

To identify the maximum tolerated dose (MTD) of stereotactic body radiotherapy (SBRT) in locally advanced pancreatic cancer (LAPC) patients who have not developed distant progression after induction chemotherapies per standard of care.

The primary objective is to determine the MTD of SBRT after for patients with LAPC (induction FOLFIRINOX and nab-paclitaxel and gemcitabine per standard of care). This will be accomplished by the standard 3+3 dose escalation design. Dose limiting toxicities (DLT) are defined by \geq Grade 3 treatment-related GI toxicity within 3 months of SBRT. These include: (1) Bowel (includes bowel perforation, obstruction, or hemorrhage) and (2) Stomach (bleeding ulcer, perforation) as determined by imaging or endoscopic evaluation.

13.2 Secondary objectives:

13.2.1 To preliminarily assess the 2 year local control, progression free and overall survival rates for LAPC patients after induction chemotherapy and SBRT. Patterns of failure will also be investigated.

Patients will be followed approximately every 3 months after SBRT. To assess recurrence, serum CA19-9 level will be obtained at each visit and CT or MRI imaging will be obtained every 3 months (\pm 2 weeks) until 12 months, and then every 6 months (\pm 4 weeks) for year 2.

Local control (LC) will be measured from completion of SBRT to the time of identification of any local progression by imaging or surgical exploration. Overall

survival (OS) will be measured from completion of SBRT until death due to any cause. Progression free survival (PFS) will be measured from completion of SBRT to the time of tumor progression or death due to any cause. PFS and OS will be estimated using the method of Kaplan and Meier. The pattern of patients experiencing local, distant or local with distant failure will be estimated using competing risks method. First site of failure will be recorded.

13.2.2. To identify early changes in the normal small intestine after SBRT for LAPC using pCT derived parameters to document changes in tissue perfusion kinetics and heterogeneity that predict for development of gastrointestinal toxicity such as duodenal ulcers, strictures, or enteritis.

We will measure changes in the perfusion/permeability related parameters of peripancreatic small intestine before, during and after SBRT for LAPC using pCT and correlating these changes with the development of gastrointestinal toxicity such as duodenal ulcers, strictures, or enteritis. Patients will undergo baseline, post-first-fraction SBRT and post-treatment CT scans on the Siemens AS Open scanner in the Department of Radiation Oncology. Perfusion/permeability parameters reflect the rate of exchange of I and include K^{trans} (transfer rate of contrast agent between vascular space and extravascular and extracellular space (EES), v_e and v_p (volume fraction of EES and vascular space, respectively), F (blood flow at the capillary level), and τ (mean transit time across capillary) [68, 74]. These derived parameters will be measured at baseline and re-measured for comparison on post-treatment scans. Patients will be followed approximately every 3 months after SBRT. Follow-up evaluations will include history and physical with assessment for presence of late toxicity using NCI CTCAE v 4.0.

The region of interest (ROI) will be placed by an experienced radiologist on the entire tumor. Tumor margins will be evaluated by reviewing all prior imaging, including CT and possible conventional MR sequences (T1 and T2). For pancreas cancer, the actual tumor extent is unknown, especially after treatment, so the ROI placement will be inherently limited by interobserver variability, which can be studied on its own.

Data will only be analyzed if seen on functional images. ROI's will be placed on the entire tumor. Tumor heterogeneity will be addressed by measuring standard deviation and skewness of the derived metrics. The experienced radiologist will draw the ROI on the normal tissue. A physicist and radiologist will review the images being acquired together to ensure the same region ROIs are covered in pre and post treatment images. The results from the study will provide the minimum size deemed measurable for the derived metrics.

13.2.3 *To investigate vascular and cellular changes resulting from SBRT for LAPC using pCT derived parameters that can predict treatment response and to assess any correlation between these pCT derived parameters and local control and progression-free survival.*

We will measure changes in diffusion and perfusion/permeability related parameters. Comparisons will be made between the pre-treatment, post-first-fraction SBRT and post-treatment pCT (K^{trans} , v_e and v_p , F , and τ) derived parameters. The baseline measurements as well as intra- and post-treatment changes in these parameters will be correlated to disease response of the primary tumor, as defined by RECIST 1.1 i.e. complete response (CR), partial response (PR), stable disease (SD) and progressive disease (PD). K^{trans} is a reproducible biomarker of response in cancers such as brain, prostate and breast tumors and has been comprehensively investigated. We expect similar results in this study. However, the other metrics derived from pCT are exploratory in nature.

Progression free survival and local control for LAPC patients treated with FOLFIRINOX followed by SBRT will be determined as described in 12.2.1. The clinical outcomes will be compared with finding on pCT. Each MRI biomarker outcome will be studied for potential association with local control and progression-free survival.

We will use ROI analysis with mean parameter values to see which measure correlates better with disease response. We will analyze heterogeneity using voxel based analysis by measuring the standard deviation and skewness.

13.2.4. *To evaluate Quality of Life (QOL) in terms of global QOL, physical symptoms, physical functioning and emotional well-being after induction chemotherapy and SBRT. Testing will be 14 days prior to SBRT, 10-12 weeks after SBRT, and 6 months after SBRT.*

The primary objective of the QOL study is to document the patient's experience of treatment for locally advanced pancreatic cancer by examining global QOL, physical symptoms, physical functioning and emotional well-being at baseline, during treatment, and after treatment. Subjects will be giving 2 questionnaires: (1) EORTC-PAN26 and (2) EORTC-QLQ-C30. The two questionnaires have a total of 56 questions, 54 out of which have answers on a scale of 1-4 and 2 questions have answers on a scale of 1-7.

QOL measures including EORTC-QLQ-C30[80] and the Pancreatic Cancer subscale (EORTC-PAN26)[81] will be assessed 14 days prior to SBRT (Time 0), 10-12 weeks

after SBRT (Time 1), and 6 months after SBRT (Time 2). The primary QOL endpoints include the EORTC global QOL, physical symptoms, physical functioning and emotional well-being.

14.0 CRITERIA FOR REMOVAL FROM STUDY

- Development of an intercurrent medical condition or need for concomitant treatment that precludes further participation in the trial
- Unacceptable toxicity or any adverse event that precludes further participation in the trial
- Patient is not treated according to the prescription dose
- The investigator removes the patient from the trial in the best interests of the patient
- Patient death
- Study completion or discontinuation
- Patient withdraws consent to continued participation in the trial or is lost to follow-up

15.0 BIOSTATISTICS

15.1 Dose Escalation Study and Clinical Outcomes Analysis

The primary objective of this trial is to determine the maximum tolerated dose (MTD) of SBRT after at least 3 months of induction chemotherapy for patients with LAPC. Dose limiting toxicities (DLT) are defined by \geq Grade 3 treatment-related GI toxicity within 3 months of SBRT. These include: (1) Bowel (includes bowel perforation, obstruction, or hemorrhage) and (2) Stomach (bleeding ulcer, perforation). We will employ a modified 3+3 dose-escalation scheme.

Dose escalation will be evaluated after 3 evaluable patients who have completed 90 days of follow-up. Due to dropout during the 90-day follow-up period, up to 6 patients may be accrued at each dose level to yield a cohort of at least 3 evaluable patients. The dose level will be escalated if none of the evaluable patients followed for 90 days exhibits any DLT within 90 days of completion of SBRT. If a DLT is observed in one patient, an additional cohort of patients will be treated at that dose to achieve having at least 6 evaluable patients at that dose level. The dose will be escalated if none of the additional patients exhibits any DLT (i.e. at most 1 DLT is observed at that dose level). Dose-escalation stops and the previous dose will be considered the MTD if 2 or more patients have a DLT. If the previous dose level has been administered to fewer than 6 patients, an additional cohort of patients will be enrolled to achieve having at least 6 evaluable patients at that dose level. If at most 1 DLT is observed among all evaluable patients treated at that dose level, that dose level will be declared to be the maximum tolerated dose (MTD). If, however, there are a total of 2 or more DLTs, the dose will be de-escalated again. The MTD will be the greatest dose at which at least 6 evaluable patients are treated with at most 1 of them experiencing a DLT.

If 3 patients have completed the 90 day follow-up without a DLT and there have been more patients accrued at that dose level, the dose may be escalated based on 0 DLTs among the first 3 evaluable patients. However, if one of the additional patients treated at the lower dose subsequently experiences a DLT, the dose escalation will halt. At that point accrual will continue at the lower

dose level to achieve a total of 6 evaluable patients who have completed the 90 day follow up at the lower dose; if at most 1 of all patients at that dose level experienced a DLT then dose escalation occur and accrual at the higher dose level will resume. If 2 or more patients have a DLT at that level, the previous dose will be considered the MTD (as described above).

For this design, the probability of escalation is as follows:

True toxicity rate	5%	10%	15%	20%	25%	30%	40%	50%
Probability of escalation	0.97	0.91	0.81	0.71	0.60	0.49	0.31	0.17

Dose escalation will start with dose level 1 (9 Gy x 3 fractions) and increase by 1 Gy per fraction at each dose level, dose level 2 will be 10 Gy x 3 fractions and dose level 3 will be 11 Gy x 3 fractions. The maximum number of patients needed for this dose escalation design is 18. A patient must be successfully treated according to prescription dose before he/she can be evaluated for the safety point, otherwise he/she will be replaced by a new patient. We expect to finish the enrollment (up to 18 patients) within 3 years. All toxicity profiles will be summarized and tabulated by dose level.

For the first secondary objective, the 2 year local control (LC) rate, progression free-survival (PFS), overall survival (OS) and patterns of failure for LAPC patients after induction chemotherapy and SBRT will be assessed using survival analysis tools such as Kaplan-Meier method or cumulative incidence curves if competing risks exist. To provide some simple comparison to the historical efficacy rates we will focus on OS due to its simplicity. The historical 2-year OS rate is approximately 20% and we expect to improve it to 40% by using the proposed treatment modality. Thus we expect that, out of the 22 patients at MTD level, we shall have at least 8 patients surviving beyond 2 years. Under the null hypothesis of 20%, the probability of observing at least 8 patients surviving beyond 2 years (i.e., type I error rate) is 5.6%. Due to the small sample size and lack of power, we will not use “at least 8 patients (out of 22) surviving beyond 2 years” as a formal decision rule for declaring the success of this study. The anticipation of at least 8 patients (out of 22) surviving beyond 2 years is merely to provide us a preliminary estimation of the efficacy signal relative to the historical control in this population.

For the above efficacy secondary objective, patients at different dose levels will be examined separately.

For the two secondary objectives involving pCT parameters (see Section 12 for details of how to obtain these parameters), all relative changes (i.e., percentage of change from the baseline, note that there will be two sets of changes, one based on the 90-minute CT and the other the 6-week CT) will be computed and correlated with the toxicity and response at

6 months post-SBRT by logistic regression. For correlation with OS, LC and PFS, survival analysis tools such as Cox model or Fine-Gray competing risks regression model will be used. For these two objectives all patients will be combined for statistical analyses.

For the QOL objective, patients will be assessed at the following time points: within 14 days prior to SBRT (Time 0); 10 to 12 weeks after SBRT (Time 1), and 6 months after SBRT (Time 2). Questionnaires will be administered in the clinic or by e-mail at all assessments. The quality of life assessment will include quality of life measures (EORTC QLQ-C30 Quality of Life Questionnaire) and the Pancreatic Cancer subscale (EORTC-PAN26). See Section 12 for more details about the quantification of the answers. The time required to complete the assessment is 20 minutes. Analysis of the QOL outcomes will be descriptive. Summary statistics will be used to characterize the patient's experience of treatment. Means, standard deviations, medians, and ranges of the QOL endpoints (scales and subscales) will be tabulated by dose level and by assessed time.

For the last secondary objective, we will assess the feasibility of obtaining adequate cytology samples for next generation sequencing using sample proportion (the number of patients who yielded sufficient material for next generation sequencing at any three time points divided by the number of patients who went through the procedure) and its confidence intervals. All patients will be combined for this objective.

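### The trigger for expanding the previous dose level counts patients treated, while the MTD definition counts evaluable patients, so a level with 6 treated, 0 DLTs and 3–5 evaluable has no consistent outcome

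*Combined protocol and SAP*

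**What the plan says.** All the relevant rules are in section 15.1 of the combined protocol and SAP.

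- **Treated and evaluable are separate counts.** Because of dropout in the 90-day follow-up, "up to 6 patients may be accrued at each dose level to yield a cohort of at least 3 evaluable patients".
- **Escalation can rest on three evaluable patients.** If more have been accrued at the level, "the dose may be escalated based on 0 DLTs among the first 3 evaluable patients".
- **Too much toxicity at the next level.** "Dose-escalation stops and the previous dose will be considered the MTD if 2 or more patients have a DLT".
- **Trigger for expanding the previous level.** "If the previous dose level has been administered to fewer than 6 patients, an additional cohort of patients will be enrolled". The stated aim is "to achieve having at least 6 evaluable patients at that dose level".
- **Declaration.** "If at most 1 DLT is observed among all evaluable patients treated at that dose level", that level is declared the MTD. The sentence gives no minimum number evaluable.
- **Closing definition.** "The MTD will be the greatest dose at which at least 6 evaluable patients are treated with at most 1 of them experiencing a DLT".
- **Replacement.** "A patient must be successfully treated according to prescription dose before he/she can be evaluated for the safety point"; a patient who fails this condition is replaced. The rule does not mention patients treated as prescribed who are then lost during the 90 days.

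**The concern.** The trigger is the only step in this sequence that counts patients who received the dose. The plan itself foresees levels where six patients have been treated and fewer are evaluable, and section 14.0 lists death, withdrawal of consent and loss to follow-up as reasons for removal. At such a level the trigger is not met, so the expansion that would bring it up to the required number never starts.

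This rule produces the primary result. In the affected case two careful readers could report different results from the same data. One names the level as the MTD on 3–5 evaluable patients; the other says that no MTD is established at that level.

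**Working it through.** **1. The plan's own figures.** For a 3+3 design in evaluable patients with true DLT rate p, the probability of escalation is (1−p)³ + 3p(1−p)² × (1−p)³. At p = 20% this is 0.512 + 0.384 × 0.512 = 0.7086. Across the eight rates in the table (5, 10, 15, 20, 25, 30, 40 and 50%) the results are 0.9734, 0.9061, 0.8138, 0.7086, 0.5999, 0.4943, 0.3093 and 0.1719. All eight agree with the plan after rounding. The table counts evaluable patients and does not involve the expansion of a previous level, so the point below does not affect it.

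**2. The affected case.** Take a previous level with 6 treated and m evaluable, m = 3, 4 or 5, followed by 2 or more DLTs at the next level.

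| Rule in 15.1 | Count used | Result |
|---|---|---|
| Stop and step back | DLTs at the next level | Previous dose is considered the MTD |
| Expansion trigger | Treated: 6, not fewer than 6 | No expansion |
| Declaration | DLTs among the m evaluable | Level is declared the MTD |
| Closing definition | Evaluable: m, fewer than 6 | Level cannot be the MTD |

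The previous level must have 0 DLTs. With 1 DLT, 15.1 already requires 6 evaluable patients before escalation, or a halt to reach 6 evaluable if the DLT appears after escalation.

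**3. How often six treated give 3–5 evaluable.** The documents give no dropout rate, so I assume independent dropout with probability d. The number evaluable is then Binomial(6, 1−d). At d = 10%, the terms for 5, 4 and 3 evaluable are 0.354 + 0.098 + 0.015 = 0.467.

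| Assumed d | P(3–5 evaluable, given 6 treated) |
|---|---|
| 5% | 26.5% |
| 10% | 46.7% |
| 20% | 72.1% |
| 30% | 81.2% |

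**4. Whether the missing expansion could change the answer.** Starting from 0/m, k = 6 − m more evaluable patients are needed. The MTD is overturned if at least 2 of them have a DLT, with probability 1 − (1−p)^k − kp(1−p)^(k−1). For k = 3 and p = 20%: 1 − 0.512 − 0.384 = 0.104.

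| Start | p = 20% | p = 30% | p = 40% |
|---|---|---|---|
| 0/3 | 10.4% | 21.6% | 35.2% |
| 0/4 | 4.0% | 9.0% | 16.0% |
| 0/5 | 0 | 0 | 0 |

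**5. The stated maximum.** The maximum of 18 equals 3 levels × 6 patients. To expect 6 evaluable, 6/(1−d) must be treated: 6/0.9 = 6.7, so 7, at 10% dropout, and 6/0.7 = 8.6, so 9, at 30%. For three full levels, 18/0.9 = 20 and 18/0.7 = 25.7, so 26.

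**The case against.** The strongest reply is that the intent is plain. The trigger sentence states its own aim of 6 evaluable patients, the declaration sentence follows directly and can be read as referring to the expanded group, and the closing definition governs. Nothing forbids enrolling further patients. This stands as evidence of what was meant and of how to repair the text. It does not remove the conflict, because the aim is attached to a condition that is false in this case.

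A second reply is that the case is uncommon, and it stands in part. If patients are added one at a time only to replace dropouts, the third evaluable patient is the sixth treated with probability 10(1−d)³d³: 0.1%, 0.7%, 4.1% or 9.3% at 5%, 10%, 20% or 30% dropout. Accrual during the 90-day wait can raise this, but the target in section 7.0 (18 in 3 years) averages about 1.5 patients per 90 days. If all 10–15 eligible patients a year enrolled, it would be about 2.5–3.7.

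A third reply is that a small evaluable group is not always weaker evidence than the plan accepts. This stands. The upper limit of the exact two-sided 95% interval for the DLT rate is 71% after 0/3, 60% after 0/4 and 52% after 0/5, against 46% after 0/6. The plan also accepts 1/6, where it is 64%. Only 0/3 is less reassuring than that.

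A reader might infer that every level with six treated and fewer evaluable is caught, or that 27–81% is the chance that the trial meets the problem. The documents support neither: the previous level must have 0 DLTs, the next level must have 2 or more, and the percentages take six treated as given.

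**Conclusion.** The inconsistency is real but narrow. It concerns the wording of the rule behind the primary result, and no sentence in 15.1 settles the affected case. It should be fixed before DLT data arrive.

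Its practical weight is mainly at 0/3, where completing the level would overturn the MTD in roughly one case in ten at a 20% true DLT rate and one in three at 40%. It is smaller at 0/4. At 0/5 the missing patient cannot change the conclusion, although the definition is still not met.

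The conditional probabilities rest on assumed dropout of 5–30%, independent between patients; the overall chance of the conflict cannot be obtained from the documents. A reader might also infer that the published escalation probabilities are wrong. They are not: they reproduce exactly to two decimals.

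**What to change.** Reconcile the sentences in 15.1 so that the expansion trigger, the declaration rule and the MTD definition count the same patients. One way is a trigger of fewer than 6 evaluable patients at the previous dose level, which matches the stated target of the expansion and the closing definition. The ceiling of 6 accrued patients for a first cohort is a different count and should remain distinguishable from it.

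In the same revision, check the stated maximum of 18 against 6 evaluable patients per level, with an explicit dropout assumption.

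The cost is 1–3 more evaluable patients at one level, possibly with more enrolled to allow for dropout. The MTD definition already requires these patients. The escalation table needs no change.
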